4.1.3 Visit window for safety and PRO assessments

Time windows will need defining for any presentations that summarise values by visit. The following conventions should also apply:

- The time windows should be exhaustive so that data recorded at any time point has the potential to be summarised. Inclusion within the time window should be based on the actual date and not the intended date of the visit.
- All unscheduled visit data should have the potential to be included in the summaries.
- The window for the visits following baseline will be constructed in such a way that the upper limit of the interval falls half way between the two visits (the lower limit of the first post-baseline visit will be Day 2). If an even number of days exists between two consecutive visits then the upper limit will be taken as the midpoint value minus 1 day.

For example, the visit windows for vital signs data are:

- Day 15, visit window 2 - 21
- Day 29, visit window 22 – 35
- Day 43, visit window 36 - 49
- Day 57, visit window 50 – 63

- Day 71, visit window 64 – 77
 - Day 85, visit window 78 – 91
- For summaries showing the maximum or minimum values, the maximum/minimum value recorded on treatment will be used (regardless of where it falls in an interval).
- Listings should display all values contributing to a time point for a patient.
- For visit based summaries:
 - If there is more than one value per patient within a time window then the closest value to the scheduled visit date should be used, or the earlier in the event the values are equidistant from the nominal visit date. If there are two values recorded on the same day and the parameter is CTCAE gradeable then the record with the highest toxicity grade should be used. Alternatively, if there are two records recorded on the same day and the toxicity grade is the same (or is not calculated for the parameter) then the average of the two records should be used. The listings should highlight the value for that patient that went into the summary table, wherever feasible. Note: in summaries of extreme values all on-treatment values collected are used including those collected at unscheduled visits.
 - To prevent very large tables or plots being produced that contain many cells with meaningless data, for each treatment group visit data should only be summarised if the number of observations is greater than the minimum of 20 and $> 1/3$ of patients dosed.
- For summaries at a patient level, all values should be included, regardless of whether they appear in a corresponding visit based summary, when deriving a patient level statistic such as a maximum.
- Baseline will be defined as the last non-missing measurement prior to the first dose of study treatment. For the re-treatment period baseline is similarly defined as the last non-missing measurement prior to the first dose on the re-treatment period. For laboratory data, any assessments made on day 1 will be considered pre-dose. If there are two visits equally eligible to assess patient status at baseline (e.g., screening and baseline assessments both on the same date prior to first dose with no washout or other intervention in the screening period) with assessment time missing, the average can be taken as a baseline value. For non-numeric laboratory tests (ie some of the urinalysis parameters) where taking an average is not possible then the best value would be taken as baseline as this is the most conservative. In the scenario where there are two assessments on day 1, one with time recorded and the other without time recorded, the one with time recorded would be selected as baseline.

- Where safety data are summarised over time, study day will be calculated in relation to date of first treatment.

Missing safety data will generally not be imputed. However, safety assessment values of the form of “< x” (i.e., below the lower limit of quantification) or > x (i.e., above the upper limit of quantification) will be imputed as “x” in the calculation of summary statistics but displayed as “< x” or “> x” in the listings. Additionally, adverse events that have missing causality (after data querying) will be assumed to be related to study drug.

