##### **6.4.8.1 Pulse and blood pressure**

Blood pressure and pulse will be collected before, during and after the infusion at the following times (based on a 60-minute infusion):

- At the beginning of the infusion (at 0 minutes)
- Every 15 minutes during the infusion (at 15, 30, and 45 minutes) (all  $\pm 5$  minutes)

- At the end of the infusion (at 60 minutes  $\pm$ 5 minutes)
- In the 1-hour observation period post-infusion: 30 and 60 minutes after the infusion (ie, 90 and 120 minutes from the start of the infusion) ( $\pm$ 5 minutes).

If the infusion takes longer than 60 minutes then BP and pulse measurements should follow the principles as described above or more frequently if clinically indicated.

The date and time of collection and measurement will be recorded on the appropriate eCRF.

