3.4.4 Vital signs

Vital signs data obtained up until the 30 days from date of last dose of study treatment will be used for reporting. Change from baseline in vital signs variables will be calculated for each

post-dose visit on treatment. For derivation of post baseline visit values considering visit window and to handle multiple records, derivation rules as described in Section 4.1.3 below will be used. The denominator in vital signs data should include only those patients with recorded data.

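### The SAP's same-day-record and visit-window rules blend or discard blood pressure and pulse readings taken during and after infusion, and give Day 1 readings after infusion start no by-visit window

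*SAP*

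**What the plan says.** Protocol 6.4.8.1 takes blood pressure and pulse at the start of the infusion, "Every 15 minutes during the infusion (at 15, 30, and 45 minutes"), at its end (60 minutes), and 30 and 60 minutes later. On a 60-minute infusion that is 0, 15, 30, 45, 60, 90 and 120 minutes. The date and time of each reading are recorded.

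SAP 3.4.4 covers their handling by cross-reference: "For derivation of post baseline visit values considering visit window and to handle multiple records, derivation rules as described in Section 4.1.3". It calculates change from baseline for each post-dose visit.

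SAP 4.1.3 sets three rules that matter here:

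- **Several values in a window.** The value nearest the scheduled date is used, and the earlier one if two are equally near.
- **Two values on the same day.** If "the parameter is CTCAE gradeable then the record with the highest toxicity grade should be used". If "the toxicity grade is the same (or is not calculated for the parameter) then the average of the two records should be used".
- **Windows.** The general principle is "The time windows should be exhaustive so that data recorded at any time point has the potential to be summarised". However, "the lower limit of the first post-baseline visit will be Day 2", and the vital-sign example opens with "Day 15, visit window 2 - 21".

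The safety baseline is the last non-missing value before the first dose. SAP 4.2.4.4 tabulates vital signs as absolute values and change from baseline per scheduled measurement, with optional box plots by week. It names no infusion time point and no minimum or maximum.

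**The concern.** Serial readings around an infusion can show a transient fall or rise. A by-visit value that averages them, or keeps only the first, shows little or none of that change. If they are averaged, the reported change from baseline also combines two different quantities: drift in the resting value between visits, and the response to that day's infusion.

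The first infusion is treated worst. Its readings after the start are post-dose, so they are not baseline, and they come before Day 2, so they are in no window.

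These tables carry some weight. Vital signs including blood pressure and pulse are a named secondary safety outcome (Protocol 2.2), and infusion-related and hypersensitivity reactions are adverse events of special interest (Protocol 5.5.3.1). Protocol 6.4.3 limits the reporting of vital-sign deterioration as an adverse event largely to changes that are serious or lead to discontinuation, on the ground that the study report will summarise vital signs. Associated symptoms are reported separately. An asymptomatic infusion-related change would therefore be expected to show mainly in the vital-sign summaries.

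**Working it through.** **1. Reproduce the windows.** Inputs from SAP 4.1.3: the first window opens on Day 2, and each upper limit is the midpoint to the next visit minus 1 day. Visits fall on Days 15, 29, 43, 57, 71 and 85; the next, Day 99, follows from the two-weekly schedule.

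- (15 + 29)/2 − 1 = 21
- (29 + 43)/2 − 1 = 35
- (43 + 57)/2 − 1 = 49
- (57 + 71)/2 − 1 = 63
- (71 + 85)/2 − 1 = 77
- (85 + 99)/2 − 1 = 91

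This gives 2–21, 22–35, 36–49, 50–63, 64–77 and 78–91, exactly as the SAP lists. Day 1 is in none of them.

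**2. Which same-day branch applies.** SAP 3.4.2 assigns CTCAE grades to laboratory variables. SAP 3.4.4 and 4.2.4.4 assign none to vital signs, so the averaging branch is the relevant one. It speaks of two records, and the protocol yields about seven. SAP 3.4.3 gives triplicate ECGs their own rule (the mean of the three); vital signs have no equivalent.

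**3. If the average is extended to seven readings.** Take a patient whose pre-infusion value that day equals baseline. If k of the 7 readings change by d, the visit value changes by k × d / 7.

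| Pattern | k | d (mmHg) | Change in visit value (mmHg) |
|---|---|---|---|
| One reading | 1 | 20 | 20/7 = 2.9 |
| Both post-infusion readings | 2 | 20 | 40/7 = 5.7 |
| 30 and 45 min | 2 | 30 | 60/7 = 8.6 |
| 15, 30 and 45 min | 3 | 20 | 60/7 = 8.6 |
| 15 to 120 min | 6 | 20 | 120/7 = 17.1 |

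The third and fourth rows are different episodes that give the same visit value. The falls of 20 and 30 mmHg are assumed for illustration.

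**4. Sensitivity to the count.** Protocol 6.4.8 may imply a separate pre-infusion reading as well as the 0-minute one. With eight readings, 30 mmHg at two of them becomes 60/8 = 7.5, and 20 mmHg at one becomes 20/8 = 2.5. With only two records, the case the rule was written for, 20 mmHg at one becomes 20/2 = 10.

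**5. If the tie-break is used instead.** All seven readings share a date and are equally near the scheduled day. The earliest, at 0 minutes, is kept, and the six later readings do not enter the by-visit value.

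**6. Day 1.** The pre-dose reading can serve as baseline. The other 7 − 1 = 6 readings have no window. Over a full course of 26 doses there are 26 × 7 = 182 planned readings, so 6/182 = 3.3% are affected, and all of them belong to the first exposure.

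**7. Is there another planned vital-sign summary?** SAP 4.1.3 lets maximum and minimum summaries use every on-treatment value whatever the window. SAP 3.4.2 defines such extremes for laboratory parameters. SAP 3.4.4 and 4.2.4.4 plan none for vital signs.

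**The case against.** The strongest reply is that the SAP never tells anyone to average seven readings. It refers to two records, so the dilution figures rest on an extension of the text. That stands. What the documents show is that the routine protocol case has no stated rule, and that both obvious ways of filling the gap lose the infusion response.

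A reader might infer that the tables cannot show infusion-related change at all. The documents do not support that. Averaging reduces the change without removing it. SAP 4.2.4.4 refers to scheduled measurements, which could be read as the protocol's infusion time points. Against that reading, SAP 3.4.4 defines change per visit and the optional plots are by week. The text is ambiguous.

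A reader might also infer that the first infusion is dropped altogether. That is not supported either. The Day 1 pre-dose value is kept as baseline, the window rules govern by-visit presentations only, and nothing keeps the later Day 1 readings out of listings or extreme-value summaries.

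Other routes exist. SAP 4.2.4.1 tabulates infusion-reaction adverse events and events of special interest, SAP 3.4.1 provides for medical review of vital-sign data, and SAP 4.2.4 allows further safety summaries. These limit the consequence. However, the adverse event tables depend on what is reported as an event, and the further summaries are discretionary.

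Two further points also stand. Protocol 5.5.2.1 presents these readings as monitoring of dosing, and no text commits to an aggregate within-infusion analysis. A group mean would dilute an uncommon reaction even without same-day averaging, which is why a per-patient extreme is needed alongside means by time point.

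**Conclusion.** The point holds as an undefined rule with a predictable loss of information. For by-visit tables of blood pressure and pulse, the stated rules either blend the infusion-day readings or keep only the first. The six Day 1 readings after infusion start fall in no window, contrary to the section's own principle that windows be exhaustive.

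If the average is extended to seven readings, a transient change appears at between one seventh and six sevenths of its size. The 8.6 mmHg example assumes seven readings, a 30 mmHg fall at two of them, and a pre-infusion value equal to baseline. The choice of the averaging branch assumes that vital signs are ungraded, as the SAP leaves them; if blood pressure were treated as gradeable, the highest-grade record would be used.

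The consequence is confined to descriptive safety tables. The same rules apply to both blinded arms, and no endpoint test, alpha level or power is affected. It should be corrected because it concerns a named safety outcome and the data are already collected.

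**What to change.** Change SAP 3.4.4, 4.1.3 and 4.2.4.4 as follows:

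- Exempt blood pressure and pulse from same-day averaging, and use the pre-infusion reading as the visit value. If a separate pre-infusion reading and a 0-minute reading are both recorded, state which one counts.
- Add one summary of blood pressure and pulse by nominal infusion time point (15, 30, 45, 60, 90 and 120 minutes) as change from that day's pre-infusion value. Include Day 1.
- In the same output, give the largest within-infusion fall and rise per patient, by treatment arm.

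The cost is SAP wording and one extra output. No new data are needed, because every reading already has a date and time.

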4.2 Analysis Methods

Table 8 details which endpoints are to be subject to formal statistical analysis, together with pre-planned sensitivity analyses making clear which analysis is regarded as primary for that endpoint.

Table 8 Formal statistical analyses to be conducted and pre-planned sensitivity analyses

Endpoints Analysed	Notes
Overall Survival	
 • Co-primary analysis using a stratified log-rank test • Sensitivity analysis using a Kaplan-Meier plot of time to censoring where the censoring indicator of the primary analysis is reversed – attrition bias • Additional analysis using Cox proportional hazards models to determine the effect of covariates on the HR estimate • Additional analysis using Cox proportional hazards models to determine the consistency of treatment effect between subgroups via the approach of Gail and Simon 1985. • Subgroup analysis using Cox proportional hazards model

Table 8 **Formal statistical analyses to be conducted and pre-planned sensitivity analyses**

Endpoints Analysed	Notes
Progression Free Survival	
 • Co-primary analysis using stratified log-rank test using BICR data (RECIST 1.1) • Sensitivity analyses using BICR data (RECIST 1.1) 
 – Interval censored analysis – evaluation time bias – Analysis using alternative censoring rules – attrition bias • Sensitivity analysis stratified log-rank test using site investigator tumour data (RECIST 1.1) – ascertainment bias • Sensitivity analysis stratified log-rank test using BICR data (RECIST 1.1, modified for confirmation of progression) – confirmation bias • Additional analysis using Cox proportional hazards models to determine the effect of covariates on the HR estimate • Additional analysis using Cox proportional hazards models to determine the consistency of treatment effect between subgroups via the approach of Gail and Simon 1985. • Subgroup analysis using Cox proportional hazards model • Exploratory analysis stratified log-rank test using BICR tumour data (irRECIST)
Proportion of patients alive at 24 months	Kaplan-Meier estimates of survival at 24 months and p-value (following the method described by Klein et al 2007)
Objective Response Rate	Fisher’s exact test using BICR data (RECIST 1.1) Sensitivity analysis using the Fisher’s exact test using site investigator tumour data (RECIST 1.1) Sensitivity analysis using the Fisher’s exact test using BICR tumour data (RECIST 1.1, modified for confirmation of progression) Exploratory analysis using the Fisher’s exact test using BICR tumour data (irRECIST)
Duration of Response	Analysis following the method described by Ellis et al 2008 using BICR tumour data (RECIST 1.1)
Proportion of patients alive and progression free at 12 and 18 months	Kaplan Meier estimates of progression free survival at 12 and 18 months
Time from randomisation to second progression	Stratified log-rank test
Time to death or distant metastasis	Stratified log-rank test using site BICR tumour data (RECIST 1.1)

Table 8 Formal statistical analyses to be conducted and pre-planned sensitivity analyses

Endpoints Analysed	Notes
Symptom improvement rate (EORTC QLQ-C30 and LC13 endpoints)	Logistic regression
HR QoL/Function improvement rate (EORTC QLQ-C30 endpoints)	Logistic regression
Time to HR QoL/Function deterioration (EORTC QLQ-C30 endpoints)	Stratified log-rank test
Time to symptom deterioration (EORTC QLQ-C30 and LC13 endpoints)	Stratified log-rank test
Change from baseline (EORTC QLQ C30 and LC13; EQ-5D-5L health state utility values and Visual Analogue Scale)	Mixed model repeated measures analysis

BICR Blinded Independent Central Review; EORTC QLQ-C30 European Organisation for Research and Treatment of Cancer 30-item core quality of life questionnaire; EQ-5D-5L EuroQoL 5 dimension, 5 level health state utility index; irRC Immune-related response criteria; LC13 Lung Cancer Module; HR QoL Quality of Life; RECIST Response Evaluation Criteria In Solid Tumours.

All outputs will be summarised by treatment arm as randomised for all ITT patients.

4.2.1 Co-primary efficacy endpoints

4.2.1.1 Overall survival

The primary analysis of the co-primary endpoint, OS, will occur when approximately 491 deaths have occurred (approximately 70% maturity). OS will be analysed using a stratified log-rank test adjusting for age at randomisation (<65 vs ≥65 years of age), sex (male vs female), and smoking history (smoker vs non-smoker) for generation of the p-value and using the Breslow approach for handling ties (Breslow, 1974).

The effect of treatment will be estimated by the hazard ratio (HR) together with its corresponding (1-alpha adjusted)% CI and p-value for the ITT population.

The covariates in the statistical modelling will be based on the values entered into IVRS at randomisation, even if it is subsequently discovered that these values were incorrect. In addition a sensitivity analysis will be produced which use the covariates recorded in the CRF.

The HR and CI can be estimated from the stratified log-rank as follows (Berry et al 1991, Collett 2003, Sellke and Siegmund 1983):

$$HR = \exp\left(\frac{U}{V}\right)$$

$$95\% \text{ CI for HR} = \left(\exp\left\{\frac{U}{V} - \frac{1.96}{\sqrt{V}}\right\}, \exp\left\{\frac{U}{V} + \frac{1.96}{\sqrt{V}}\right\} \right)$$

Where $U = \sum_k U_k = \sum_k \sum_i (d_{1ki} - e_{1ki})$ is the stratified log-rank test statistic obtained from the SAS LIFTEST procedure, $\sqrt{V} = \sqrt{\sum_k V_k}$, is its standard deviation, k denotes the stratum and d_{1ki} and e_{1ki} are the observed and expected events in Group 1, stratum k.

Kaplan-Meier plots of OS will be presented by treatment arm. Summaries of the number and percentage of patients who have died, those still in survival follow-up, those lost to follow-up and those who have withdrawn consent will be provided along with the median OS for each treatment. The assumption of proportionality will be assessed.

Proportional hazards will be tested firstly by examining plots of complementary log-log (event times) vs log (time) and, if these raise concerns, by fitting a time-dependent covariate to assess the extent to which this represents random variation. If a lack of proportionality is evident, the variation in treatment effect will be described by presenting piecewise HR calculated over distinct time-periods. In such circumstances, the HR can still be meaningfully interpreted as an average HR over time unless there is extensive crossing of the survival curves. If lack of proportionality is found, this may be a result of treatment-by-covariate interactions, which will be investigated.

Sensitivity analyses

A sensitivity analysis for OS will examine the censoring patterns to rule out attrition bias, achieved by a Kaplan-Meier plot of time to censoring where the censoring indicator of OS is reversed.

The number of patients prematurely censored will be summarised by treatment arm. A patient would be defined as prematurely censored if their survival status was not defined at the DCO.

In addition, duration of follow-up will be summarised using medians:

- In censored patients who are alive at DCO only: Time from randomisation to date of censoring (date last known to be alive) for each arm.
- In all patients: Time from randomisation to the date of death or to the date of censoring for censored patients, regardless of treatment.

Subgroup analyses

Subgroup analyses will be conducted comparing OS between treatments in the following subgroups of the FAS:

- Age at randomisation (<65 vs \geq 65 years of age)
- Sex (male vs female)
- Smoking status (smoker vs non-smoker).
- Stage of disease at study entry (Stage III A vs Stage III B).
- Histology (squamous vs all other).
- Best response to prior anticancer therapy (CR, PR, SD).
- Type of chemotherapy 1 (gemcitabine-based vs non- gemcitabine -based).
- Type of chemotherapy 2 (cisplatin-based vs carboplatin-based).
- Time from last dose of radiation to randomization (<14 days, \geq 14 days).
- WHO performance status at baseline (normal activity [PSTAT=0] vs restricted activity [PSTAT=1]).
 - This will be determined from the response to “Performance status” (PSTAT module) on the eCRF at screening. Patients with a missing performance status will be included in the ‘restricted activity’ category.
- Region (Asia, Europe, South America vs North America).
 - This will be determined from the centre number (CENTRE). If there are less than 20 events in the “South America” category, these patients will be combined with those in North America.
- Race (White, Black/African-American, Asian, Other [Native Hawaiian/Pacific Islander or American Indian/Alaska Native or Others]).
 - This will be determined from the response to “Race” (DEM module) on the eCRF at screening.
- PD-L1 status (\geq 25% vs <25%).
 - Only samples with sample date on or before first dose should be used

- for multiple evaluable samples with sample date on or before the first dose, the sample with the highest PD-L1 % tumour membrane staining result should be used
- EGFR (positive vs negative)

The subgroup analyses will be based on values recorded on the eCRF.

Other baseline variables may also be assessed if there is clinical justification or an imbalance is observed between the treatment arms. The purpose of the subgroup analyses is to assess the consistency of treatment effect across expected prognostic factors.

No adjustment to the significance level for testing will be made since all these subgroup analyses will be considered exploratory and may only be supportive of the primary analysis of OS.

For each subgroup, the HR and 95% CI will be calculated from an unstratified Cox proportional hazards model with treatment as only covariate. The Cox models will be fitted using SAS® PROC PHREG with the Efron method to control for ties, using the by statement to obtain HR and 95% CI for each subgroup level separately.

These hazard ratios and associated two-sided 95% CIs will be summarised and presented on a forest plot, along with the results of the overall primary analysis.

If there are too few events available for a meaningful analysis of a particular subgroup (it is not considered appropriate to present analyses where there are less than 20 events in a subgroup), the relationship between that subgroup and OS will not be formally analysed. In this case, only descriptive summaries will be provided.

Effect of covariates on the HR estimate

Cox proportional hazards modelling will be employed to assess the effect of covariates on the HR estimate for the primary treatment comparison. A model will be constructed, containing treatment and the stratification factors alone, to ensure any output from the Cox modelling is likely to be consistent with the results of the stratified log-rank test.

The result from the initial model and the model containing additional covariates will be presented.

Additional covariates for this model will be age at randomization, sex, smoking status, stage of disease at study entry, histology, best response to prior anticancer therapy, WHO performance status, region and race.

The model will include the effect regardless of whether the inclusion of effect significantly improves the fit of the model providing there is enough data to make them meaningful.

Consistency of treatment effect between subgroups

Interactions between treatment and stratification factors will also be tested to rule out any qualitative interaction using the approach of [Gail and Simon 1985](#).

Impact of switching (crossover outside of this study) to immunotherapies (or other potentially active investigational agents) on OS analyses

Exploratory analyses of OS adjusting for the impact of subsequent immunotherapy or other treatment may be performed, if a sufficient proportion of patients switch.

Methods such as Inverse Probability of Censoring Weighting ([Robins 1993](#)), Rank Preserving Structural Failure Time ([Robins and Tsiatis 1991](#)), and other methods in development will be explored as appropriate. The decision to adjust and the final choice of methods will be based on a blinded review of the data and the plausibility of the underlying assumptions. Additional supportive analysis by censoring the treatments switchers at the time of initiation of subsequent therapy will also be conducted. These analyses are intended to further support the OS benefit and reimbursement appraisals.

Baseline and time-dependent characteristics will be explored, and summaries of baseline characteristics will be provided by treatment arm, splitting between those that have and haven't switched at the time of the analyses.

Subsequent therapies received after discontinuation of treatment will be summarised and listed by treatment group. Patients who subsequently received an immunotherapy agent or entered an immunotherapy trial will be summarised and listed by treatment arm according to line of subsequent therapy, i.e. immediately after immunotherapy or as a later line.

